1.0 Background

Diabetes is a leading cause of kidney failure, heart disease, stroke, visual impairment, and non-traumatic lower limb amputations. Diabetes self-care and preventative health services can prevent or delay many diabetes-related complications, yet few patients consistently receive all recommended services or engage in recommended self-care behaviors that are challenging to implement and sustain. Patient activation (i.e., knowledge, skills and confidence to manage their own health and care) is essential to achieving optimal diabetes self-management and is associated with lower costs.

By providing an engaging and convenient means to track and visualize health data, obtain education and guidance, and connect patients and doctors, patient portals offer a promising platform to increase patient activation, enhance care and promote self-management while overcoming the limitations of costly and difficult to scale face-to-face interventions. We recently applied user-centered design sprint methodology and key strategies for patient engagement to develop a patient portal intervention for patients with diabetes called the Diabetes Dashboard (also known as My Diabetes Care).

The Diabetes Dashboard is embedded within an established patient portal, My Health at Vanderbilt (MHAV). The Diabetes Dashboard is a multi-faceted intervention designed to help patients better understand their diabetes health data as well as support self-management. The Diabetes Dashboard uses graphics to visualize and summarize patients' diabetes health data, incorporates motivational strategies (e.g., social comparisons), and provides literacy-level sensitive educational resources. The Diabetes Dashboard is grounded in a well-established Chronic Care Model adapted for eHealth (i.e., healthcare practices supported by electronic processes and communication). By leveraging elements within the Model's five domains (self-management support, delivery system design, decision support, clinical information systems, and eHealth education), the Diabetes Dashboard has the potential to create more informed and activated patients leading to improved outcomes.

2.0 Rationale and Specific Aims

In order to assess dashboard usability, usage patterns, and user experience over time, and to uncover errors in dashboard functionality prior to a larger interventional trial, we will conduct a longitudinal usability study. The study will utilize questionnaires to quantify participants' perceptions and responses to the dashboard and semi-structured interviews to comprehensively assess users' experience and barriers to use. Combining qualitative and quantitative assessments of usability identifies more usability concerns than quantitative (e.g., questionnaires) assessments alone. Each participant will have access to the dashboard for 1 month from the time of enrollment. This duration allows sufficient time for participants to become familiar with the dashboard and determine if and how to use the dashboard in the management of their diabetes.

In the current study, we aim to assess: (1) the usability and acceptability of the Diabetes Dashboard, (2) users' attitudes about dashboard features and potential improvements, and (3) the potential impact of the dashboard on secondary cognitive and behavioral outcomes including patient activation.

3.0 Inclusion/Exclusion Criteria

Participants will be eligible for the study if they have type 2 diabetes mellitus, are currently being treated with at least one diabetes medication, are able to speak and read in English, are age 21 or over, have an existing MHAV (i.e., Vanderbilt patient portal) account, and self-report reliable access to a computer with internet access.

We will exclude patients living in long term care facilities, patients with known cognitive deficits, patients with severe visual or hearing impairment, patients with unintelligible speech (e.g., dysarthria), and patients currently participating in another diabetes related research study.

4.0 Enrollment/Randomization

Participants will be able to complete an electronic consent form and enroll online via Research Electronic Data Capture (REDCap) version 5.0.8.

5.0 Study Procedures

Setting. The Vanderbilt Adult Primary Care (VAPC) clinics and Eskind Diabetes Clinics are located within a large ambulatory care facility in Nashville, TN. An electronic health record (Epic Systems Corp.) stores all clinical data and patients receive access to their clinical data via an integrated and highly-adopted patient web portal, MHAV, that is accessible on desktops and via a native mobile app for iOS and Android mobile operating systems.

Participants and Recruitment. Potential participants will be identified automatically using VUMC's *Subject Locator* to query the EHR for patients with upcoming clinic appointments who meet the discrete inclusion and exclusion criteria. We will send identified patients a letter describing the study. Study flyers will be placed in participating clinic sites. Interested patients will contact a research assistant to learn more about the study and confirm eligibility.

Participants will complete an electronic consent form and enroll online via REDCap. Our target enrollment is 70 participants. In accordance with best practices and to reflect a range of patient experience with diabetes and groups with distinct usability needs, we will recruit a purposive sample to achieve at least 20% representation of each of the following characteristics: (a) limited health literacy and (b) age 65 or over. Some participants may have one or more of these characteristics. Health literacy will be assessed using a validated on one-item screener that asks respondents to rate their confidence independently filling out medical forms. Consistent with prior studies, we will categorize participants noting any lack of confidence filling out medical forms as having limited health literacy.

Data Collection and Outcome Measures. Study participants will complete questionnaires electronically via email using REDCap at two time points: enrollment (T₀) and end of study (T₁). The enrollment questionnaire (T₀) will include basic demographic questions, items about computer/smartphone usage, and validated measures of health literacy and eHealth literacy. Both questionnaires will contain

validated scales to assess study outcomes. Participants will be compensated \$40 for completing the enrollment questionnaire, \$35 for completing the study end questionnaire, and \$5 for first 10 minutes of dashboard use.

The primary outcome measures will be: (a) ease of use and satisfaction as assessed by the System Usability Scale at T₁, (b) user experience as assessed by end of study questionnaire and semi-structured interviews at T₁. Secondary outcomes will include system usage (total number of dashboard visits, total duration of dashboard use, and use of embedded educational links, secure messaging, and a link to the American Diabetes Association Online Community) and the potential impact of the dashboard on the following secondary cognitive and behavioral outcomes assessed using validated scales at T₀ and T₁: patient activation, diabetes self-efficacy, diabetes knowledge, diabetes care understanding, diabetes self-care, and diabetes distress.

At the conclusion of their one month of dashboard access, we will conduct one-on-one, semi-structured interviews with a subsample of at least 10 participants. This methodology is most appropriate for in-depth assessment of patients' perceptions and reactions regarding a proposed intervention. Interviews are preferred over focus groups for understanding usability because focus groups can amplify bias and individual opinions. Interviews will take place by phone or in person and will last approximately 30 minutes. A trained interviewer will use a semi-structured interview guide to facilitate the interview and elicit in-depth understanding of participants' perceptions and experiences with specific dashboard functionality as well as barriers to use. Additional participants will be enrolled until saturation is reached. Saturation will be defined as no new usability concerns raised in the preceding two interviews and typically occurs between 10 and 30 interviews. Participants will be compensated an additional \$40 for the interview.

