6.0 Statistical Analysis Plan

Statistical Analysis. We will use descriptive statistics to characterize the study participants and survey responses. We will use a one sample t-test to compare the mean SUS score at T₁ to the threshold score of 68 indicative of "above average" usability and a two-sample t-test to compare SUS scores of independent groups (e.g., participants with limited vs. adequate health literacy). If SUS score distributions suggests asymmetry or nonnormality, we will use the one sample median test to compare the median SUS scores at T₁ to the threshold score of 68 and Wilcoxon-Mann-Whitney test to compare the SUS score distributions of two independent groups.

To assess whether there was a significant improvement in the continuous secondary cognitive/behavioral outcomes from baseline to end of study (T₀ to T₁), we will perform two-sided paired t-tests on the pairwise differences. If any of the distributions of pairwise differences suggest asymmetry or nonnormality, the non-parametric Wilcoxon Signed Rank Sum test will be performed in lieu of paired t-tests. We will use the McNemar's test for to compare paired proportions and Fischer's Exact test for independent proportions. All analyses will be completed using statistical software under the supervision of a biostatistician in the Vanderbilt Center for Diabetes Translational Research (CDTR).

Sample Size. In the context of the primary outcome, SUS score, and assuming a standard deviation of 12 based on prior studies, with a sample size of 50, a one sample t-test would detect an absolute difference in mean SUS scores of at least 5 points above the threshold score of 68 with 82% power. Conservatively assuming study dropout of 20%, we aim to enroll 70 participants.

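### Does recruiting patients who have upcoming clinic appointments mean that clinic visits must be recorded and analysed alongside the T0 to T1 changes?

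*Combined protocol and SAP*

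**What the plan says.** Section 5.0 gives two recruitment routes. One is to "query the EHR for patients with upcoming clinic appointments who meet the discrete inclusion and exclusion criteria" and send those patients a letter. The other is passive: "Study flyers will be placed in participating clinic sites". The section gives no look-ahead window for the query and does not tie the enrollment questionnaire (T0) to the appointment date.

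Section 2.0 sets the observation period: "Each participant will have access to the dashboard for 1 month from the time of enrollment". No comparison group is described. Section 4.0 has randomization in its heading, but its whole content is "Participants will be able to complete an electronic consent form and enroll online via Research Electronic Data Capture (REDCap) version 5.0.8".

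The third aim in section 2.0 is to assess "the potential impact of the dashboard on secondary cognitive and behavioral outcomes including patient activation". Section 5.0 repeats this as "the potential impact of the dashboard on the following secondary cognitive and behavioral outcomes" and names six: patient activation, self-efficacy, knowledge, care understanding, self-care and distress. For the continuous scales section 6.0 states "we will perform two-sided paired t-tests on the pairwise differences", with a signed-rank test if the differences look non-normal. The plan does not mention clinic visits between T0 and T1.

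**The concern.** A visit to primary care or a diabetes clinic could move several of these scales without any help from the dashboard. The query favours people who are due such a visit, and the window that follows is short. A paired test measures mean change from every cause, so a visit effect would be counted together with any dashboard effect. Other causes of change, such as retesting, time trends and regression to the mean, are hard to observe. A visit could at least be looked up in the record already used for recruitment, and the plan does not do so.

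At stake is the reading of the third aim. A significant improvement might be carried into the later interventional trial as early evidence that the dashboard works. The System Usability Scale (SUS) and user-experience outcomes are assessed at T1 and do not rest on change from baseline, so they are not exposed to this.

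**Working it through.** **Inputs from section 6.0.** SUS standard deviation 12, difference 5 points, n = 50, power 82%; then "Conservatively assuming study dropout of 20%, we aim to enroll 70 participants". Alpha is not stated; two-sided 0.05 is assumed.

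**The plan's own figure.** One-sample t-test, noncentrality = (5/12) × √50 = 2.946, df = 49. Power = 82.3%, which agrees with the stated 82%. This concerns SUS only; no power is given for the six scales.

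**Completers.** 70 × 0.80 = 56.

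**How much could visits matter?** Suppose the dashboard has no effect, a share *f* of participants has a visit, and a visit shifts their change score by *e* SD of change. Then the mean change is *f* × *e*, its SD is √(1 + *f*(1 − *f*)*e*²), and the noncentrality is mean/SD × √56. Neither *f* nor *e* is in the documents; both are assumptions. The chance that one scale is significant is:

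| Share with a visit | e = 0.1 | e = 0.2 | e = 0.3 |
|---|---|---|---|
| 10% | 5.1% | 5.2% | 5.6% |
| 25% | 5.4% | 6.6% | 8.5% |
| 50% | 6.6% | 11.3% | 19.4% |
| 100% | 11.4% | 31.3% | 59.7% |

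The range runs from negligible to large. The largest figure needs every participant to have a visit inside the month. The documents do not suggest this: flyers require no appointment, and a queried appointment could fall before T0 or after T1. These are also not false positives of the planned test. Its null hypothesis is zero mean change, and wherever *f* × *e* is above zero that null is false. They become errors only if a significant result is read as causal.

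**Would recording visits help?** Take an assumed even split of the 56, 28 with a visit and 28 without. The 95% CI half-widths, in SD of change, are:

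- all 56: t(0.975, 55)/√56 = 2.004/7.483 = 0.268
- 28 without a visit: t(0.975, 27)/√28 = 2.052/5.292 = 0.388
- difference, 28 versus 28: t(0.975, 54) × √(2/28) = 2.005 × 0.267 = 0.536

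Power is 0.20 for a 0.3 SD difference between the groups, and 0.33 for a 0.3 SD change within the 28 without a visit. A null difference would not clear the visit of blame. A change confined to the no-visit group would still be uncontrolled.

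**Is the split itself sound?** A visit that takes place after T0 is a post-baseline event. Section 1.0 presents portals as a way of connecting patients with doctors, and section 5.0 counts secure messaging among the usage outcomes. Dashboard use could therefore prompt a visit, and stratifying on visits could remove or distort part of the very effect of interest.

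**The case for a change.** The best case for a change is that this goes beyond the usual complaint about single-arm studies. The plan's own recruitment filter makes a visit more likely, the cause is identifiable from records already in use, and acting on it would take two data fields, one descriptive table and some wording. The word potential is the only hedge, and section 6.0 sets beside it a test for significant improvement. Since a larger trial is to follow, a significant result could be over-read.

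Part of this stands. The plan nowhere says outright that these results are uncontrolled and not causal, and a sentence to that effect would do no harm. The share with a visit is unknown partly because nobody plans to count it.

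The rest does not lead to a change. The conclusion on the third aim would have to be worded in the same way whatever the visit data showed, so collecting them would alter no result and no interpretation. Calling the tests unadjusted also misses the mark, because covariate adjustment cannot supply the missing comparison group. The cost is less certain than it looks: the plan describes using the record to find patients, and whether extraction after enrollment is covered cannot be seen from the available text.

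**Conclusion.** The observation is correct, but the plan needs no change. Paired tests in a single-arm study show within-person change from any cause, and the appointment filter adds one possible cause to several that would remain without it. Its contribution could be trivial (about 5–9% against 5% for shares of 10–25% and effects of 0.1–0.3 SD) or substantial (about 60% if everyone has a visit worth 0.3 SD). Those figures rest on assumed shares and effects, 56 completers, no dashboard effect and two-sided alpha of 0.05.

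The claim the plan makes is already modest. Section 2.0 describes a longitudinal usability study that precedes a larger interventional trial. The scales are secondary, section 6.0 frames the test as change from baseline to study end, and no success or progression rule depends on them. Analysts reporting an uncontrolled before-after comparison would ordinarily list its limits, clinic visits included. If they choose to describe appointments, one already scheduled at T0 is the safer variable, because it is fixed at baseline; the share should be reported descriptively, with no inference from a split.

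### The interview stopping rule does not carry over the two groups the plan singles out at enrollment, so a saturation claim may be unsupported for limited-literacy or older users.

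*Combined protocol and SAP*

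**What the plan says.** Section 5.0 (Participants and Recruitment) sets out a purposive sample, with the stated aim "to reflect a range of patient experience with diabetes and groups with distinct usability needs". The condition is "at least 20% representation of each of the following characteristics: (a) limited health literacy and (b) age 65 or over". It governs recruitment, for which "Our target enrollment is 70 participants".

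Later in Section 5.0, user experience is primary outcome (b), assessed by the end-of-study questionnaire and by interviews. The plan provides for "semi-structured interviews with a subsample of at least 10 participants". The continuation rule is "Additional participants will be enrolled until saturation is reached", and the stopping rule is "Saturation will be defined as no new usability concerns raised in the preceding two interviews". The plan adds that saturation "typically occurs between 10 and 30 interviews".

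Section 5.0 does not say how interviewees are chosen from those enrolled, and it sets no minimum per group for the interviews. Section 7.0 codes all interviews under six elements of user experience and does not mention the two groups.

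**The concern.** The two parts of Section 5.0 rest on different premises. Recruitment treats limited-literacy and older users as likely to meet different problems. The stopping rule treats every interviewee as interchangeable: any two consecutive interviews without a new concern end the series. If the recruitment premise is right, two quiet interviews with younger people of adequate literacy say little about whether problems are exhausted among the others.

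The interviews feed a primary outcome, and under Section 7.0 they inform possible revisions of the dashboard. Section 2.0 places the study ahead of a larger interventional trial. A difficulty particular to one of these groups and missed here could go into that trial uncorrected. The quantitative plan does allow for the distinction, since Section 6.0 gives limited versus adequate health literacy as its example of a SUS comparison. The interview plan has no counterpart.

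**Working it through.** The plan gives no figure for interviewees per group, so there is none to reproduce on this point. Its one computed figure, 82% power for the SUS test, reproduces (82.3% with a two-sided 5% level, which is assumed because the level is not stated) and plays no part here.

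**Inputs from the plan.** Enrollment is 70 and assumed dropout is 20% (Section 6.0), so 70 × 0.80 = 56 completers. The floor for each group is 20% of those enrolled, 0.20 × 70 = 14. At the same share among completers, 0.20 × 56 = 11.2, taken as 11. The minimum number of interviews is 10.

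**Assumptions not in the plan.** Interviewees are drawn from completers without regard to group, and dropout is the same in and out of the group.

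**One group.** The number of group members among n interviewees is hypergeometric with N = 56 and K = 11. For n = 10:

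- P(none) = C(45,10) / C(56,10) = 3,190,187,286 / 35,607,051,480 = 0.0896
- P(exactly one) = 11 × C(45,9) / C(56,10) = 9,747,794,485 / 35,607,051,480 = 0.2738
- P(at most one) = 0.0896 + 0.2738 = 0.363

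**Range, same formula.**

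| Group members | Interviews | None | At most one |
|---|---|---|---|
| 11 of 56 | 10 | 9.0% | 36.3% |
| 12 of 56 | 10 | 7.0% | 30.9% |
| 14 of 70 | 10 | 9.0% | 35.7% |
| 10 of 50 | 10 | 8.3% | 34.9% |
| 14 of 56 (25%) | 10 | 4.1% | 21.7% |
| 17 of 56 (about 30%) | 10 | 1.8% | 11.9% |
| 11 of 56 | 15 | 2.1% | 13.4% |
| 11 of 56 | 20 | 0.4% | 3.8% |

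**Either group absent from 10 interviews.** With 11 people in each group, the answer depends on how far the groups overlap, which the plan does not give.

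- Complete overlap: 0.0896, or 9%.
- No overlap: 2 × 0.0896 − C(34,10) / C(56,10) = 0.1792 − 0.0037 = 0.1755, just under 18%.
- If absence of one group is independent of absence of the other: 1 − (1 − 0.0896)² = 0.171, which lies near the top of this range.

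**The two interviews that trigger the stop.** Considering composition alone, two randomly drawn interviewees include nobody from a given group with probability (45/56) × (44/55) = 0.643.

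**What these figures measure.** They describe who is interviewed. Stopping at 10 also needs the last two interviews to raise nothing new. Under the stated assumptions, the chance of stopping at 10 with a given group absent therefore cannot exceed 9%, and with at most one member heard it cannot exceed 36%.

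**The case against.** The headline figures combine three unfavorable conditions: the fewest interviews allowed, the lowest group share allowed, and selection blind to group. The plan says at least 10 interviews, expects saturation somewhere from 10 to 30, and sets 20% as a minimum. The table shows how fast the risk shrinks away from that corner. This stands, and the figures should be quoted with their range.

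Blind selection is an assumption. The enrolled sample is purposive and literacy is measured at enrollment, so the team may intend to choose interviewees in the same way. The documents establish neither method. What stands is that nothing in the written rule would prevent a stop with a group unheard.

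A reader might infer that a saturation claim missing one of these groups would be wrong, or that the groups would go unheard altogether. The documents support neither. Absence from the interviews does not show that unreported problems exist. All participants are also to be given the end-of-study questionnaire, which is part of the same primary outcome, and the SUS. That softens the gap without closing it, because Section 2.0 itself holds that questionnaires alone find fewer usability problems than a combined assessment.

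Finally, no hypothesis test, power statement or safety decision depends on the rule. That limits how serious the point is. It does not make the rule consistent with the recruitment design.

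**Conclusion.** The point holds as a mismatch within Section 5.0. The groups that justify purposive recruitment have no place in the interview subsample or in the stopping rule, so saturation can be declared without evidence about them. Such a claim would be unsupported for the missing group; it would not be shown to be false.

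At the minimum of 10 interviews and about a 20% share, with group-blind selection and equal dropout, a given group is absent with probability 9% and has at most one member heard with probability 36%. At least one of the two groups is absent with probability between 9% and just under 18%, depending on overlap. More interviews or a larger share reduce these figures considerably. A reader might take 9% or 36% as the probability of a premature stop. They are only ceilings on the chance of stopping at 10 with that composition, under these assumptions.

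The change is worth making because it touches a primary outcome and costs little. It does not threaten the study's quantitative conclusions.

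**What to change.** In Section 5.0, state how interviewees are chosen and make the stopping rule group-aware:

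- Select interviewees purposively from the literacy and age data collected at enrollment, so that each of the two groups makes up at least 20% of interviews. That means at least two of the first 10; one person may count for both groups.
- Do not declare saturation until the two most recent interviews in each group, as well as the two most recent overall, have raised nothing new.
- Report how many interviewees came from each group alongside any statement about saturation.

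This applies the plan's own 20% share and two-interview criterion within the groups, so it needs no new threshold. Two per group is a floor and not a guarantee. If a problem affected half of a group, two interviewees from it would both miss it with probability 0.5² = 25%.

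The cost is a few sentences of protocol text and possibly some further interviews. For example, if the latest interviewee in each group raised something new at interview 10, at least two more would be needed with complete overlap and four with none, or $80 to $160 at $40 each, plus interviewing and coding time. The quantitative sample size and analyses are unaffected.
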